The entire pilot study phase for this project will be completed over the course of six months. We plan to enroll 30 adolescents, aged 16-19 to playtest our game. We will meet with participants between 2-4 times for approximately 1-1.5 hours each time, over the course of two to four weeks. Participants will complete baseline measures, two gameplay sessions and a post-assessment to measure feasibility, acceptability, and usability. Each participant will complete the pilot study within two to four weeks. We will meet with them after school in a classroom (securing room with coordination from our school partners). When the study is introduced to parents/guardians and students, we have always stressed that a stipulation of our studies requires reliable transportation to/from our studies. In certain cases, we will provide a bus pass.

All participants will be assigned a study identification number to link pre/post assessments and to conduct focus groups. Data collection and storage will be conducted according to standardized protocols. The link between participant's identity and the study number is confidential and will be kept separate from all study data. Research data, such as informed consents/assents, transcriptions, and field notes, is kept in cabinets that are locked except when in use, and access to

data stored in computers is password protected. We will collect participants' names, school, gender, grade level, age, race, and ethnicity. Names will not be sent to any third parties. Any data shared with NIH or other third-party organizations will be aggregate data. We will collect this information and it will be stored in a secured database.

The Yale University Human Subjects Committee (the committee that reviews, approves, and monitors research on human subjects) may inspect study records. All published results will be group data. Information that will be collected during the focus group interviews will be erased 12 months after the completion of the study and after review of their content has been completed.

1. Formative and development work: (1 year)

- a.) We will work iteratively with our target audience of 16-19-year old adolescents within schools to develop videogame content, collecting qualitative data for the videogame intervention and refining our logic model with input from 8 focus groups of 5 adolescents each (n=40), aged 16-19 and 4 focus groups of 5 young adults aged 18-25 (n=20).

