The subject population for this project is adolescents between the ages of 16-19. Young adults aged 18-25 will be recruited for focus groups as well. There are also adults (19-80) that will be recruited to participate in separate focus groups at the Convention.

For this study, 8 focus groups of 5 adolescents each (n = 40), boys and girls in Connecticut, aged 16-19 will participate in the focus groups and 30 adolescents, boys and girls, aged 16-19 will participate in the pilot testing of the adapted game (2 groups of 3 adolescents will participate virtually and 6 groups of 4 adolescents each will participate in person at their school site while following COVID-19 guidelines). These adolescents will be recruited from the high schools that we already have established partnerships with, such as Maloney High and Hamden High. In addition, we will conduct 4 focus groups of young adults aged 18-25 (N=20) in Connecticut. These young adults will be recruited from local universities. Additionally, 30 youth (16-19) over the course of two years (e.g., meeting annually) from the national School-Based Health Alliance (SBHA) National Convention will also be recruited to participate in focus groups for the project.

For the focus groups with the adults, 50 adults (19-80) who are affiliates of the SBHA will be recruited over the course of two years (e.g., meeting annually) during the national SBHA Convention to participate in the project and will receive information sheets. Their role represents various positions within school-based health centers across the nation. Their role in this study is to be part of our focus groups to help inform game development and implementation strategies.

For the individual interviews, up to 20 participants aged 16-25 who are currently receiving treatment for opioid use disorder will be recruited to participate in this study. The Director of Research at the APT Foundation has approved and will post flyers (see example of the flyer attached) on site at the APT Foundation. Other interview participants may be recruited through provider referral. Interested participants will contact our research team to participate.

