The potential risks associated with this study have to do with maintenance of the confidentiality of the identities of the participants enrolled in the study and information relating to them. As with all of our studies, we will train study researchers in maintaining confidentiality. Prior to the start of the focus group, researchers will discuss potential risks including breach of confidentiality. Examples include but are not limited to informing participants at the beginning of focus groups of risks related to confidentiality and the sensitive nature of the topic, by conducting focus groups in a private classroom in the school, by training and reviewing questions with our team of experts who specialize in addiction medicine, and by informing study participants via information sheets of the risks of confidentiality breaches. Discussion topics will focus on interested content to build out narratives for game development. Participants will be encouraged to only disclose what they are comfortable sharing and to consider sharing suggestions for building out a videogame intervention as opposed to confidential information about themselves. De-identified hard copies of any data will be stored in locked cabinets and electronic data will be stored in secure, password-protected computers. Only the PI and other relevant research staff will have access to the data.

Playing the **PlaySmart** game or engagement in discussions with the research team about its content may pose a potential psychological risk in that we address sensitive issues around drug use and its consequences. The research staff will be available to provide assistance to all participants, answer their questions, and serve as a resource if any distress or concern arises. The assessments and instruments may also present a potential risk given that some of the questions are sensitive in nature and address issues around drug use and risky behaviors. Again, the research staff will be available to assist the participants and the program site staff if there appears to be any distress around the questions being asked and connect them to appropriate school personnel.

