Participants in the young adult focus groups will be over the age of 18 and will provide verbal consent before the group commences.

For the interviews with individuals in treatment for Opioid Use Disorder: Individuals who express interest in being interviewed (via text, email and/or a phone call) will schedule a brief phone call screening with a research assistant who is a member of our research team. During the phone call, the research assistant will verify that the individual meets eligibility criteria (e.g., between the ages of 16-25, receiving treatment for an opioid use disorder, a device to access the internet for the virtual interview and be able to sit for 60-90 minutes in an interview). If the individual meets this criteria and is a minor, our team will request parent/guardian contact information at the conclusion of the screening call in order to obtain parental/guardian consent from individuals between 16-17 before scheduling an interview. With their parent/guardian contact information, a member of our research team will schedule a phone call with a parent/guardian to describe the study. We will then provide an electronic version of the parent/guardian consent to the parent/guardian. Once we receive the appropriate signature, we will schedule an interview with the minor. If the individual is aged 18-25, an interview will be scheduled with them immediately after the screening portion of the phone call.

For interviews with treatment: Individuals will express interest in being interviewed to our team via text, email, or phone call. A research assistant from our team will screen the potential participant via a brief phone call or email. The research assistant will verify that the interested individual is a treatment provider, and they have treated individuals aged 16-35 for opioid use disorder in the last 5 years. If the individual meets this criteria, they will then be scheduled for a virtual interview with our research team. Our team will ensure that the participant has access to internet and an appropriate device.

7. Evaluation of Subject(s) Capacity to Provide Informed Consent/Accent: Indicate how the personnel obtaining consent will assess the potential subject's ability and capacity to consent to the research being proposed.

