A number of precautions will be actively integrated into the research procedures to protect the confidentiality and anonymity of all participants. As we have done with our other videogame intervention studies, a Certificate of Confidentiality will be automatically provided by the National Institute on Drug Abuse upon their granting the award. All research staff participating in the study will be required to complete training in research ethics. Data collection forms will be designated by ID numbers only. A separate master file of names, addresses, contact persons, and telephone numbers, along with the study ID numbers will be maintained in a locked file cabinet in the PI's research offices. All data entry and analyses will be completed with ID numbers only. The study will be explained to others, such as the parent/guardian and program staff as a study of child development that will focus on promoting healthy behaviors. In instances in which data are requested from other sources or it is beneficial to the participant to provide information to another individual or agency (e.g. medical personnel) this will only be done with the written permission of the parent/guardian on a "Release of Information" form stipulating who the information is provided to, or received from. The research staff will follow standard confidentiality procedures for research programs.

Any breaches of confidentiality will be reported immediately to the participant, their family, and relevant school personnel as well as the IRB and the NIDA PO as well as the HIPAA Privacy officer. Additional systems will then be instituted to prevent a similar breach from occurring.

All portable devices must contain encryption software, per University Policy 5100. If there is a technical reason a device cannot be encrypted please submit an exception request to the Information Security, Policy and Compliance Office by clicking on url <http://its.yale.edu/egrc> or email [contact]

5. What will be done with the data when the research is completed? Are there plans to destroy the identifiable data? If yes, describe how, by whom and when identifiers will be destroyed. If no, describe how the data and/or identifiers will be secured.

Data collected in the study will reside in our computerized database and electronic storage mechanisms. All data analyses will be performed under approved HIC protocols.

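### The confidentiality-breach rule sends notice to family and relevant school personnel with no limit by age or study group, although the protocol enrols adults who take part without family involvement

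*Combined protocol and SAP*

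**What the plan says.** The rule stands in Section IV, item 4, under the procedures for preventing and addressing breaches: "Any breaches of confidentiality will be reported immediately to the participant, their family, and relevant school personnel as well as the IRB". The sentence goes on to list the NIDA PO and the HIPAA Privacy officer. The same part of Section IV describes its precautions as meant to "protect the confidentiality and anonymity of all participants".

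The paragraph before the rule covers release of information to another person or agency and says that "this will only be done with the written permission of the parent/guardian". It also says: "The study will be explained to others, such as the parent/guardian and program staff as a study of child development".

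Elsewhere the protocol separates adults from minors:

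- Subject Population (item 6): "up to 20 participants aged 16-25 who are currently receiving treatment for opioid use disorder will be recruited to participate in this study".
- Process of Consent/Assent (Section III, item 6): a minor in that group needs parent or guardian consent before an interview is booked. For the others, "If the individual is aged 18-25, an interview will be scheduled with them immediately after the screening portion of the phone call".
- The same section has pilot participants aged 18-19, and emancipated minors, give their own written consent.

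On confidentiality, Risks (item 9) opens with: "The potential risks associated with this study have to do with maintenance of the confidentiality of the identities of the participants enrolled in the study". The Research Plan (item 4) says that the link between a participant's "identity and the study number is confidential and will be kept separate from all study data".

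Minimizing Risks (item 10) lists any breach of confidentiality as an adverse event and sets out a separate reporting route for adverse events.

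**The concern.** The rule suits a minor recruited at school, whose parent has been involved. For an adult who joined alone, it sends notice to people who had no part in the decision and may not know about it. The step meant to repair a breach would then pass on a further fact, participation, without the person's permission.

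The stakes are highest for adults in the treatment interviews. Current treatment for opioid use disorder is a condition of entry to that group, so a notice that identifies the group, or describes the breached content, would reveal treatment status to family. For young adults, treatment providers, stakeholders and school-based health affiliates, what would be disclosed is participation, not a health condition.

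No endpoint, sample size or analysis is affected. This is a point about participant protection.

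**Working it through.** No formula applies to the rule itself. The check sets the passages side by side, then counts the people it reaches.

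**1. Scope.** The rule covers any breach, and its section speaks of all participants. The word *relevant* qualifies school personnel. Nothing qualifies family: no age, study group or permission condition appears there or elsewhere.

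**2. Who takes part without family involvement.** Four groups are wholly adult by their age criteria (Subject Population, item 6):

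| Group | Ages | Planned maximum |
|---|---|---|
| Young adult focus groups | 18-25 | 20 |
| School-based health affiliates | 19-80 | 50 |
| Treatment providers | 19-80 | 20 |
| Stakeholders | 19-80 | 20 |

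20 + 50 + 20 + 20 = **110**.

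Four groups mix minors and adults:

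| Group | Ages | Planned maximum |
|---|---|---|
| School focus groups | 16-19 | 40 |
| Pilot | 16-19 | 30 |
| Youth Advisory Council | 16-19 in item 6; Recruitment Procedures includes college-age adults | 30 |
| Treatment interviews | 16-25 | 20 |

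40 + 30 + 30 + 20 = 120. The total is 110 + 120 = 230, and 110/230 = 48%. The adult share of the 120 is not given, so the rule reaches at least 110 adults at full enrolment, plus an unknown number up to 120. For treatment interviewees the adult count lies between 0 and 20.

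**3. What a notice to family would disclose.**

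- Wholly adult groups: participation.
- Treatment interviewees aged 18-25: participation, and treatment status if the report identifies the interview group or the content. The rule does not say what the report contains.
- Treatment interviewees aged 16-17: a parent has already consented, so participation is not news. The breached content could be.
- Adults aged 18-19 in the school, Youth Advisory Council and pilot groups: participation, where the family does not already know. Some parents may know, because Eligibility (item 8) has staff discuss the study with parents of school participants.

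**4. Two routes for one event.**

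| | Breach rule (Section IV, item 4) | Adverse-event route (item 10) |
|---|---|---|
| Participant | yes | not named |
| Family | yes | not named |
| School personnel | relevant ones | not named |
| PI and Information Security Officer | not named | yes |
| IRB | yes | yes |
| NIDA PO | yes | for reportable or serious events |
| HIPAA Privacy officer | yes | not named |

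Staff handling a breach thus have two recipient lists and no statement of how they combine.

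**5. The adjacent release rule.** It makes parent or guardian permission the only route for passing on information. An adult participant has no stated way to give or refuse permission.

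**6. A possible origin.** Section III, item 1 gives an enrolment target of 150. This equals 40 + 30 + 50 + 30 (school focus groups, pilot, affiliates, Youth Advisory Council). The difference, 230 - 150 = 80, equals the four groups of 20: young adults, treatment interviewees, providers and stakeholders. That fits with groups having been added without updating the rest of the text, but does not prove it.

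**The case against.** The best defence is context. The surrounding text refers to parents, program staff and child development, and so presumes school-age minors. The section also promises standard confidentiality procedures and a Certificate of Confidentiality. Recordings are coded by number, and speakers are told not to identify themselves. Parent contact details are requested at screening only when a treatment interviewee is a minor, so staff may hold no family contact for the adults. All of this stands, and it makes a harmful notice less likely. None of it limits the sentence, which covers any breach and names family without condition.

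Four stronger readings are tempting, and the documents do not support them:

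- *Every breach goes to a school.* The rule says relevant school personnel. Treatment interviewees are recruited at a treatment site or by provider referral and are interviewed virtually, so a school notice for them is not shown.
- *The notice itself discloses treatment.* The protocol also enrols people aged 18-25 with no treatment criterion, and the content of the report is not prescribed. Disclosure of treatment status is foreseeable, not automatic.
- *The treatment-status harm reaches 130 people (110 plus all 20 treatment interviewees).* Eligibility implies treatment for at most 20, fewer once those aged 16-17 are set aside. That 8 of the 10 eligible single-year ages are adult ages says nothing about how many participants are adults.
- *Confidentiality is the study's main risk.* Risks opens with it but goes on to psychological risk, and Section IV calls it one of the potential risks. Neither passage ranks them.

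**Conclusion.** The rule is wrong as written; this is more than a missing detail. It directs notice to the families of adults without their permission. Three parts of the protocol do not fit together: the breach rule, the adverse-event route for the same event, and a release rule with no place for an adult's own permission.

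The size is 110 participants in wholly adult groups at planned maximum, plus an unknown number of adults in the mixed-age groups. The more serious harm, disclosure of treatment status, is confined to adult treatment interviewees, between 0 and 20 people, and depends on what the report says.

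Two assumptions apply. The counts use planned maxima, not actual enrolment. The consent pages were not available for review, so it is assumed that they do not narrow the rule; even if they did, the protocol sentence would still need to agree with them.

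**What to change.** Amend the sentence in Section IV, item 4 as follows:

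- Participants aged 18 or over and emancipated minors are notified directly. Family or school personnel are told only with the participant's permission.
- For other minors, the participant and the parent or guardian are told.
- Relevant school personnel are told only about breaches that arise from school-site activities, subject to the permission condition above for adults and emancipated minors.
- The IRB, NIDA PO and HIPAA Privacy officer stay as listed.

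Add an adult participant's own written permission to the release rule in the same section. Reconcile the breach rule with the adverse-event route in Minimizing Risks (item 10), so that one breach has one list of recipients. The mandatory-reporting duties in Process of Consent/Assent are separate and unaffected.

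The cost is a short protocol amendment, with matching wording in the information sheets and consent forms where they repeat the rule. No added staff or study procedures are needed.

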The probable duration of the project is 2 years. This timeline includes formative work (e.g., focus groups and interviews), the development of a new videogame in conjunction with our videogame development partners, and piloting/playtesting of the new videogame upon completion of development.

	Year 1	Year 2
Develop PlaySmart videogame intervention		
Conduct/transcribe focus groups and interviews	X	
Analyze data and refine logic model	X	X
Develop manuals (Game Playbooks) and digital game intervention	X	X X
Pilot-test game intervention , develop user’s manual, pilot processes for subsequent RCT (during next phase of research)		X X X

3. **Background:** Describe the background information that led to the plan for this project. Provide references to support the expectation of obtaining useful scientific data.

Drug overdose is now the leading cause of death in those under the age of 50. According to the Centers for Disease Control and Prevention (CDC), 130 Americans die every day from an opioid overdose¹. These overdose mortality rates reflect the increase of opioid misuse in this country and of particular concern, is that they translate to adolescents. Opioid overdose deaths among adolescents aged 15–19 increased 253% between 1999 and 2016². Importantly, close to 40% of prescription opioid misuse and 68% of heroin use starts in adolescence and young adulthood³. Given the importance of this problem to the health and future of our youth, it is imperative to develop and implement effective strategies to prevent the initiation of opioid misuse in youth. The current situation demands high quality, evidence-informed programs that can be rapidly deployed with good fidelity. To date, programs created to prevent substance use initiation overall (e.g., alcohol, marijuana, and tobacco) do not have much impact in terms of effectively preventing initiation of opioid misuse. Further, there is conflicting evidence on the effectiveness of substance use prevention interventions, particularly those conducted in schools where many of these programs are deployed⁴. Novel ways to reach this highly vulnerable population in settings such as the over 2600 school-based health centers (school-based HCs) are needed.

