
Our study's specific aims are to:

- 1a: Develop the *PlaySmart* game through focus groups with up to 40 16-19-year old high school students, focus groups with up to 20 18-25-year-old young adults, interviews with up to 20 16-25-year olds, interviews with up to 20 opioid use disorder treatment providers and focus groups with up to 20 stakeholders (educators, prevention specialists, etc.).
- 1b: Pilot-test *PlaySmart* with 30 adolescents, using methods from our prior research ^{13,16,19,20,33}
- 1c: Develop implementation strategies and partners through focus groups with 50 School Based Health Alliance affiliates and 30 adolescents from the Youth Advisory Council.

4. **Research Plan:** Summarize the study design and research procedures using non-technical language that can be readily understood by someone outside the discipline. **Be sure to distinguish between standard of care vs. research procedures when applicable and include any flowcharts of visits specifying their individual times and lengths.** Describe the setting in which the research will take place.

This protocol will be conducted over two years. The outline below highlights the research plan. We will conduct focus groups and interviews to help inform the development of a digital intervention and then evaluate the feasibility, acceptability, and usability in a pilot study. Eight focus groups with five adolescents (n=40), aged 16-19, will be conducted locally over the course of six months. Each group will meet once for approximately 1-1.5 hours after school in a classroom. When the study is introduced to parents/guardians and students, we have always stressed that a stipulation of our studies requires reliable transportation to/from our studies. In certain cases where transportation is not available, we will provide a bus pass.

In addition, we will conduct 4 focus groups with approximately five 18-25-year-old young adults (n=20). Each focus group will meet once for approximately 1-1.5 hours at a private location on a college campus, a public meeting space such as a library, or in a location at Yale Medical School. All participants will provide consent. Our goal is to learn about the perceptions and experiences of opioid misuse among young adults to inform our intervention.

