If appropriate, has a Certificate of Confidentiality been obtained? Following newguidelines enacted in 2017, the NIDA/NIH will automatically grant a COC for this project.

SECTION V: POTENTIAL BENEFITS

Potential Benefits: Identify any benefits that may be reasonably expected to result from the research, either to the subject(s) or to society at large. (Payment of subjects is not considered a benefit in this context of the risk benefit assessment.)

It is anticipated that the young adolescents enrolled in this study should benefit directly from the study as the purpose of the study is to improve their attitudes, intentions, and knowledge, and decision-making around health promotion and opioid use. This research has the potential to benefit a large number of youth around the country and worldwide, because if in the pilot test the intervention is shown to be effective, then this intervention can be replicated elsewhere and with a greater ease of dissemination. The potential benefits to participants are great and strict precautions are being taken to protect the confidentiality and well-being of participants, as has been described above. Thus, the potential benefits to the participants outweigh the potential risks.

SECTION VI: RESEARCH ALTERNATIVES AND ECONOMIC CONSIDERATIONS

1. **Alternatives:** What other alternatives are available to the study subjects outside of the research?

No participation in the study

2. **Payments for Participation (Economic Considerations):** Describe any payments that will be made to subjects, the amount and schedule of payments, and the conditions for receiving this compensation.

Each participant (adolescents and young adults) will receive a \$30 gift card for participating in the game development focus group.

Each participant will receive a \$30 gift card for participating in the individual interviews conducted with adolescents and young adults who are currently in treatment for opioid use disorder.

Each participant will receive a \$30 gift card for participating in the individual interviews conducted with treatment providers who have treated individuals 16-35 for opioid use disorder in the last 5 years.

Participants in the pilot study will either receive a \$25 gift card for one two-hour gameplay session and follow-up questions (in person) OR two gift cards totaling \$60 for six one hour gameplay sessions and follow-up questions (virtually).

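### The protocol gives two incompatible gameplay schedules for the pilot, and its benefits text looks to a one-group pilot of 30 for evidence of effectiveness

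*Combined protocol and SAP*

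**What the plan says.** **Schedule.** Research Plan (item 4), pilot paragraph: "We will meet with participants between 2-4 times for approximately 1-1.5 hours each time, over the course of two to four weeks", and then "Participants will complete baseline measures, two gameplay sessions and a post-assessment to measure feasibility, acceptability, and usability". Payments for Participation (Section VI, item 2) pays $25 "for one two-hour gameplay session and follow-up questions (in person"), or gift cards totalling $60 "for six one hour gameplay sessions and follow-up questions (virtually"). Subject Population (item 6) gives the split: "2 groups of 3 adolescents will participate virtually and 6 groups of 4 adolescents each will participate in person at their school site".

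**Purpose.** The opening of the Research Plan says the study will "evaluate the feasibility, acceptability, and usability in a pilot study". The timetable under Probable Duration (item 2) lists, beside the pilot, work to "pilot processes for subsequent RCT (during next phase of research"), and the Research Plan's own list of pilot activities also treats the RCT as subsequent.

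**What is expected of the pilot.** Potential Benefits (Section V): "if in the pilot test the intervention is shown to be effective, then this intervention can be replicated elsewhere". The closing text of Risks (item 9) includes a reduction in participants' actual opioid misuse in the study's purpose and expected direct benefit. The consent section (Section III, item 6) labels the pilot an RCT.

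**Analysis.** Statistical Considerations (item 12) sets two-tailed tests at 0.05, adjustment of alpha for multiple tests when necessary, and an intention-to-treat sample. It names no pilot endpoint or test and does not say what may be concluded from the pilot. Section IV plans automatic logging of game progress and player decisions.

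**The concern.** There are two separate problems, and the first is the larger.

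First, the two accounts of the schedule cannot both be followed. Session number and length define how much of the intervention a participant receives, and the payments are attached to them. If the payments version is what happens, everyone who plays virtually also plays three times as long. Any difference in acceptability or usability between the modes then has two explanations, and a pooled figure describes neither exposure.

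Second, the benefits text looks to the pilot for something that its design cannot supply. All 30 participants play, and no comparator, allocation or randomisation is described. If a pre/post change were reported as significant under the general 0.05 rule, retest effects, other school activity and a wish to please the researchers would all remain possible explanations. The RCT label in the consent section could hide this from a reader, because no arms stand behind it. No misuse endpoint is defined for the pilot either, so the expected benefit of reduced misuse has no planned measure of its own.

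**Working it through.** **1. Sample size.** From Subject Population: 2 × 3 = 6 virtual and 6 × 4 = 24 in person. 6 + 24 = 30, which matches the stated pilot size. The documents give no power calculation, effect size or SD to reproduce.

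**2. The two schedules side by side.**

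| | Research Plan | Payments, in person (24) | Payments, virtual (6) |
|---|---|---|---|
| Gameplay sessions | 2 | 1 | 6 |
| Length | meetings of about 1-1.5 h | 2 h | 1 h |
| Play time per person | 2 × 1 to 2 × 1.5 = 2-3 h, if each session fills one meeting (assumption) | 1 × 2 = 2 h | 6 × 1 = 6 h |
| Total contact | 2 × 1 = 2 h to 4 × 1.5 = 6 h | not given | not given |

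- Number: neither one nor six equals two.
- Length: a two-hour session is longer than a 1-1.5 hour meeting.
- Meetings: six sessions exceed the maximum of four meetings, unless several sessions share a meeting.
- Total hours: 2 h in person lies within the implied 2-3 h. The virtual 6 h equals the Research Plan's maximum contact time, before any baseline or post-assessment.

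The firm conflict is therefore in the number and length of sessions. Total hours in person can be made to agree.

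**3. Confounding under the payments version.** Let M = 0 in person and M = 1 virtual, and let H be planned hours of play. Then H = 2 + 4M for every participant. A model with an intercept, M and H has three columns of which only two are independent. The virtual minus in-person difference equals the mode effect plus the effect of 4 extra hours: one equation with two unknowns. This holds at any sample size. A pooled mean gives weight 24/30 = 80% to 2 h of play and 6/30 = 20% to 6 h.

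**4. Attribution (illustration only).** Item 12 declares no pre/post test, and the documents give no size for a non-game shift. Assume a paired t-test, n = 30, two-sided 0.05, independent participants and no game effect. Let δ be the non-game drift in SDs of the change score. The test statistic follows a noncentral t with 29 df and noncentrality δ√30, and the critical value is 2.045.

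| Assumed δ | δ√30 | P(p<0.05) |
|---|---|---|
| 0.2 | 1.095 | 0.185 (19%) |
| 0.3 | 1.643 | 0.355 (36%) |
| 0.5 | 2.739 | 0.754 (75%) |

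For scale, the 95% CI half-width of a mean change is 2.045/√30 = 0.37 SD of the change score.

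**The case against.** The strongest reply is that the sentence in Section V is a conditional answer to a form question about benefit to society. It is not an endpoint or a decision rule. The Research Plan limits the pilot to feasibility, acceptability and usability and treats it as preparation for an RCT, and no p-value is promised as proof that the game works. This stands, and it is why the effectiveness wording is minor. A reader might infer that the sponsor plans an efficacy claim from the pilot. The documents do not support that: they contain a loose expectation and no rule that limits it.

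On the schedule, the Research Plan's pilot paragraph describes only classroom meetings, whereas other sections add virtual delivery, so that paragraph may simply not have been updated. This would explain the conflict but does not remove it, and nothing in the documents shows which schedule is intended. A reader might also infer that the contradiction undermines every pilot estimate. That goes too far, since in-person play of 2 h, which covers 24 of the 30 participants, fits the Research Plan's implied range.

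The drift probabilities rest on assumed drifts and on a test that no section declares. They also treat participants as independent, although the pilot is run in eight groups of three or four. They show what could happen and do not forecast this study's result.

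**Conclusion.** The concern holds in two parts of unequal weight.

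**Schedule: should be fixed.** The Research Plan and the payments section contradict each other on the number and length of gameplay sessions. Under the payments version, exposure differs threefold (2 h against 6 h) and coincides exactly with mode. It may be tempting to treat this as a precision problem that a larger pilot would solve, but no sample size separates mode from hours when one determines the other.

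**Effectiveness wording: minor.** A single group in which everyone plays cannot attribute a pre/post change to the game, so Section V and the misuse benefit under Risks go beyond the design. The RCT label in the consent section does not alter this, because no arms or allocation are described anywhere. The virtual and in-person groups are not a control comparison either: both play, and no random allocation between them is described. The 19%, 36% and 75% figures depend on the assumptions stated with them. The conclusion about attribution does not depend on those figures.

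**What to change.** 1. Reconcile the Research Plan with Payments for Participation on the number and length of gameplay sessions, including the payments and contact time tied to them. Report pilot results, and time played from the gameplay logs in Section IV, by mode (24 in person, 6 virtual), descriptively.
2. In Section V, replace the effectiveness wording with a statement that the pilot's feasibility, acceptability and usability results will inform the subsequent RCT and, through it, possible wider use. Under Risks, remove reduced actual misuse as an expected benefit of the pilot.
3. In Statistical Considerations, state that any pilot pre/post comparison is exploratory, is reported as an estimate with a 95% CI, and will not be used to claim effectiveness.
4. Reconcile the RCT label in the consent section with the single-group pilot in the Research Plan and Subject Population.

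**Cost.** No new participants or measures are needed, and items 2 to 4 are text changes. Item 1 may alter payments or contact time, and so what participants are told. The sponsor also gives up a possible claim based on a significant pre/post change.
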